#### **6.7.4     Prior and concomitant treatment**

During this trial medication prescribed to the subject prior to the start of the study will not be collected. All prescription medication (except minerals and vitamins), including non-study vaccines, being taken by the subjects on entry to the study and all prescription medication given in addition to the study vaccine during this clinical trial are to be regarded as concomitant medication and must be documented on the Concomitant Medications CRF.

In consideration of the overlapping Northern Hemisphere influenza vaccination campaign, the use of seasonal flu vaccines during the period 3 weeks before to 3 weeks after vaccination on Days 0 and 21 is an exclusion criterion.

All subjects may continue therapy for chronic medical conditions provided that they are not listed in section 8 of the British National Formulary (BNF) or include chloroquine, gold or penicillamine or other drugs listed in section 10.1.3 of the BNF to suppress a chronic disease process. Subjects with chronic medical conditions must be maintained on a stable regimen for at least 2 weeks prior to study entry as assessed by the medical history.

Use of other medication including over-the-counter products should be discouraged during the study. Investigational drugs are prohibited during the course of the study.

The following concomitant treatments are discouraged and, if used, might lead to a major protocol violation and result in withdrawal of the subject from the study according to the medical judgment of the lead physician (See exclusion criteria, 6.7.3; and Removal of subjects from therapy or assessments, 6.7.5):

- Systemic steroids,
- Other immunosuppressive agents,
- Blood or plasma derivatives, including immunoglobulin,
- Non-study vaccines (with the exception of post-exposure vaccinations in a medical emergency, e.g., hepatitis, rabies, tetanus) within 2 weeks.

#### **6.7.5     Removal of subjects from therapy or assessments**

The subject, or where applicable, the subject's legally acceptable representative(s) can withdraw consent for participation in the study at any time without prejudice. The investigator can withdraw a subject if, in his or her clinical judgment, it is in the best interest of the subject or if the subject cannot comply with the protocol.

In addition, a subject may not be eligible for subsequent immunization or may be discontinued from the study following occurrence of:

- Convulsions or any other neurological disturbances after vaccination,
- Hypersensitivity to the investigational vaccine,
- Other suspected side effects that could compromise the subject's wellbeing.

Any subject who, despite the requirement for adequate contraception, becomes pregnant during the trial will not receive further immunization. The site should maintain contact with the pregnant subject, and obtain pregnancy outcome information. It should be noted that pregnant women are at substantially increased risk from pandemic H1N1 influenza. WHO and ACIP recommend the administration of pandemic H1N1 vaccine to pregnant women. It is likely that the Department of Health will also recommend that pregnant women should receive pandemic H1N1 vaccine.

The subject will be followed up after withdrawal, the cause of which will be recorded in detail on the Study Termination CRF, and where appropriate, on the Adverse Events and/or Concomitant Medications CRF. Where the withdrawal of a subject resulted from an adverse event, this will be documented in accordance with the procedures in section 8.6.

Whenever possible, the tests and evaluations listed for the termination visit will be carried out.

Withdrawn subjects will not be replaced.

All subjects who have received investigational vaccines should be included in clinical events assessments, and all who provided pre-immunisation and post-immunisation blood samples at the scheduled times should be included in the immunogenicity assessments.

#### **6.7.6 Stopping/pausing rule**

There are no predetermined stopping rules other than those described above in 6.7.5.

## **7.0 VACCINES**

### **7.1 Vaccines**

All subjects in this study will be randomized to receive two doses of the two pandemic influenza vaccines purchased by the Government to confront the current H1N1 pandemic. Specifically the vaccine are:

- (a) Baxter, plain (i.e., non-adjuvanted), whole virus, vero-cell-grown, influenza A/California/2009 (H1N1) pandemic vaccine, containing 7.5µg of viral HA per 0.5mL dose (given the trade name, Celvapan);
- (b) GlaxoSmithKline, AS03-adjuvanted, split-product, egg-grown, influenza A/California/2009 (H1N1) pandemic vaccine, containing 3.75µg of viral HA and AS03 adjuvant composed of squalene, DL-α-tocopherol and polysorbate 80 (given the trade name, Pandemrix).

The vaccines will be supplied by the Department of Health as part of its initial consignment of vaccine from each manufacturer. It will be labelled, packaged, and supplied with a package information leaflet exactly as procured from the manufacturers for the Government's national pandemic influenza vaccine administration programme.

### **7.2 Vaccine labelling, storage, and packaging**

All vaccine supplies must be stored between +2°C to +8°C, protected from light. The vaccine **must not** be frozen. Vaccines that have not been stored according to manufacturer's instructions **must not** be used. In the event that the vaccine cannot be used, the vaccine must be replaced with fresh stock. The Department of Health will supply the investigational H1N1 vaccine. The investigator (or pharmacist) will make an inventory and acknowledge receipt of all shipments of study vaccine.

### **7.3 Vaccine administration**

The Principal Investigators at each study site will be responsible for the administration of the vaccine to subjects enrolled into the study according to the procedures stipulated in this study protocol. All vaccines will only be administered by personnel who are qualified to perform that function under applicable local laws and regulations for the specific study site.

The vaccine should be allowed to reach room temperature before use. The vaccine must be **gently shaken** and visually inspected before use. The vaccination site should be disinfected with a skin disinfectant (e.g., 70% alcohol). Before vaccination, the skin must be dry. **DO NOT inject intravascularly or subcutaneously.**

### **PRECAUTIONS TO BE OBSERVED IN ADMINISTERING STUDY VACCINE:**

Study vaccines should not be administered to individuals with known hypersensitivity to any component of the vaccine.

An axillary temperature  $\geq 38^{\circ}\text{C}$  or serious active infection (with fever and systemic symptoms) are reasons for delaying vaccination.

Standard immunization practices should be observed and care should be taken to administer the injection intramuscularly. As with all injectable vaccines, appropriate medical treatment and supervision should be readily available in case of rare anaphylactic reactions following administration of the study vaccine. Epinephrine 1:1000 and Chlorphenamine (or equivalent adrenalin and antihistamine agents) should be available in case of any anaphylactic reactions. Care must be taken to ensure the vaccine is not injected into a blood vessel.

#### **7.3.1 Administration of GSK Pandemrix vaccine**

*Nature and contents of container:*

Pandemrix is supplied in multidose vials (type I glass) containing 2.5 ml vaccine (antigen) suspension (10 x 0.25 ml doses) with a stopper (butyl rubber), AND vials (type I glass) of 2.5 ml adjuvant (emulsion) (10 x 0.25 ml doses) with a stopper (butyl rubber).

Prior to administration, the two components should be mixed. The volume after mixing 1 vial of suspension (2.5 ml) with 1 vial of emulsion (2.5 ml) corresponds to 10 doses of vaccine (5 ml).

*Instructions for mixing and administration of the vaccine:*

1. Before mixing the two components, the emulsion and suspension should be allowed to reach room temperature, shaken and inspected visually for any foreign particulate matter and/or abnormal physical appearance. In the event of either being observed, discard the vaccine.
2. The vaccine is mixed by withdrawing the contents of the vial containing the emulsion (Vial B) by means of a syringe and by adding it to the vial containing the suspension (Vial A).

3. After the addition of the emulsion to the suspension, the mixture should be well shaken. The mixed vaccine is a whitish emulsion. In the event of other variation being observed, discard the vaccine.
4. The volume of Pandemrix (5 ml) after mixing corresponds to 10 doses of vaccine.
5. The vial should be shaken prior to each administration.
6. Each vaccine dose of 0.5 ml is withdrawn into a syringe for injection.
7. The needle used for withdrawal must be replaced by a needle suitable for intramuscular injection.

### **7.3.2 Administration of Baxter Celvapan vaccine**

Celvapan is supplied in multidose vials (type I glass) of 5 ml suspension (10 x 0.5 ml doses) with a stopper (bromobutyl rubber). The vaccine should be allowed to reach room temperature before use. Shake before use. Each vaccine dose of 0.5 ml is withdrawn into a syringe for injection.

## **7.4 Method of assigning subjects to Baxter and GSK vaccine groups**

It would be desirable if vaccinees could be assigned Baxter and GSK vaccines at the same time, i.e., both vaccines arrived in each centre before regulatory approval (ethics and MHRA) is obtained. This may not occur, so procedures will be put in place to meet the following scenarios:

- A. Both vaccines arrive at each centre prior to regulatory approval:
- B. Only one vaccine arrives at each centre prior to regulatory approval:

### **A. BOTH VACCINES ARRIVE AT EACH CENTRE PRIOR TO REGULATORY APPROVAL**

We will use a block randomisation scheme to ensure that balance between vaccines is maintained and all volunteers are randomly allocated to groups. Subjects who meet the study admission criteria will be enrolled into the study and will be assigned a **5 digit subject number**:

The first digit identifies the study site (1 for Leicester; 2 for Nottingham; 3 for Sheffield).

The second digit reflects the age of the subjects on Day 0 (1 for 18-44; 5 for 45-64; and 9 for 65 years and older).

The following three digits identify the subject within the site and will be assigned sequentially, starting with 001 corresponding to the first subject enrolled within each age band.

Thus each centre will have three randomisation lists, each list corresponding to each age band.

Each centre will continue recruiting volunteers within an age band until the tally for the centres reaches a total of 120 subjects for that age band.

Volunteers in each age band will be randomised by a computer generated randomization code (1:1 proportions in block size(s) that will be determined by the statistician to ensure balance across groups). The randomisation code for each age band will be stored in individual, sequentially-numbered envelopes, specific for each centre, and will be opened by the nurse with responsibility for vaccine administration. The type of vaccine for administration will be printed on an adhesive label. The label will be peeled from its backing and entered into an appropriate space in the 'Vaccine Log', ensuring that the instruction and vaccine that is administered actually agree (See below).

Only one study nurse/doctor will be responsible for vaccine administration in each centre. This study nurse/doctor will be un-blinded with respect to the type of vaccine administered; he/she will play no

other role in the study. To maintain blinding, volunteers will be told to look away, both during preparation and administration of the vaccine. It is essential that volunteers do not see the syringe that is used or whether the vaccine is translucent or cloudy. The 'Vaccine' study nurse/doctor will document in the CRF: (a) the time of vaccine administration; and (b) the site of vaccine administration (LEFT or RIGHT – vaccine will normally be given into the non-dominant arm). The 'Vaccine' study nurse/doctor will record the volunteer's trial number, together with the vaccine that was administered (the adhesive label in the envelope) in the 'Vaccine Log'. The study nurse will check that the instruction in the envelope corresponds with the type of vaccine that is administered before and after each injection. He/she must inform the Principal Investigator immediately if the wrong vaccine was administered.

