#### **6.7 Study population**

##### **6.7.1 Initial approach**

We will approach staff and healthcare workers in university and healthcare settings in Leicester, Nottingham, and Sheffield either directly (i.e., personal contact), or through written information by post, email, or poster advertising. We may also request GPs to contact potentially suitable patients, either in writing or verbally, asking whether they would be prepared to learn more about the study with a view to participation. We may advertise the study through news items or advertisements on the local radio or in local newspapers. Respondents will be enrolled after they receive a detailed explanation of the study protocol and providing they meet inclusion and exclusion criteria and give signed informed consent. We will approach staff in frontline areas (acute admissions unit, acute wards, intensive care, bone marrow units) before non-health care workers are enrolled.

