#### B. ONLY ONE VACCINE ARRIVES AT EACH CENTRE PRIOR TO REGULATORY APPROVAL:

This scenario is the one most likely to occur. It will be implemented if all regulatory approval is in place, AND only one of the two trial vaccines is available in each centre, AND the second vaccine will not arrive within five days of arrival of the first vaccine. Subjects who meet the study admission criteria will be enrolled into the study and will be assigned a **5 digit subject number**:

As before the statistician would generate three 'randomisation' lists for each centre, with a list for each age band.

As before, the first digit identifies the study site (1 for Leicester; 2 for Nottingham; 3 for Sheffield);  
As before, the second digit reflects the age of the subjects on Day 0 (1 for 18-44; 5 for 45-64; and 9 for 65 years and older);

As before the next three digits identify the subject within the site.

HOWEVER, the distribution of the numbers will be randomised, with the first 60 numbers corresponding to the first vaccine to arrive (Vaccine 1), and the second 60 numbers corresponding to the second vaccine (Vaccine 2).

As an example, the first person to be vaccinated in Leicester could have the number 10054, i.e., with '1' corresponding to Leicester, '0' reflecting that he/she is aged 18-44 years, and '054' being the volunteer's unique trial number.

Each centre will continue recruiting volunteers within an age band until the tally for the centres reaches a total of 60 subjects for that age band for Vaccine 1. The same process will then be carried out with Vaccine 2, when it arrives.

Depending on the interval between arrival of GSK and Baxter vaccines, we will endeavour to ship sera from some volunteers who received Vaccine 2 in the first tranche of sera that was sent for analysis. The laboratory staff will not know when Vaccine 2 arrived and was first given, so will not know whether sera were collected from recipients of GSK or Baxter vaccine.

Vaccinees will not be told which vaccine they receive. They will be instructed to look away, both during preparation and administration of the vaccine. It is essential that volunteers do not see the syringe that is used or whether the vaccine is translucent or cloudy.

As before, only one study nurse/doctor will be responsible for vaccine administration in each centre. This study nurse/doctor will be un-blinded with respect to the type of vaccine administered; he/she will play no other role in the study.

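### Volunteer blinding for self-scored reactions relies visually on an instruction to look away; preparing the dose out of sight and masking the syringe would protect it better at little cost

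*Protocol*

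**What the plan says.** Section 7.4 A (both vaccines available): "To maintain blinding, volunteers will be told to look away, both during preparation and administration of the vaccine". It gives the reason directly afterwards: "It is essential that volunteers do not see the syringe that is used or whether the vaccine is translucent or cloudy". Section 7.4 B (one vaccine first, which the protocol expects to be the likelier case) repeats the requirement and the method: "They will be instructed to look away, both during preparation and administration of the vaccine".

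Other parts of the protocol that bear on this:

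- Section 7.3.1: the GSK product is mixed from two vials, one mixing yields 10 doses, and the needle is changed after each dose is drawn up. "The mixed vaccine is a whitish emulsion".
- Section 7.3.2: the Baxter product is a suspension drawn from one multidose vial. No mixing and no needle change are mentioned.
- Section 7.4 A and B: one un-blinded nurse or doctor per centre gives the vaccine and has no other part in the study. Section 7.4 B adds that volunteers are not told which vaccine they receive.
- Section 8.3: volunteers grade their own symptoms from 0 to 3 on diary cards and record relief medication.
- Sections 5.0 and 9.2.6: short-term reactogenicity is a secondary objective, and the incidence and severity of reactions are compared between vaccines.
- Section 6.7.1: "We will approach staff and healthcare workers in university and healthcare settings in Leicester, Nottingham, and Sheffield". Frontline staff are approached "before non-health care workers are enrolled".

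**The concern.** The protocol recognises that seeing the dose would reveal the vaccine and sets a strict requirement against it. The measure it states to meet that requirement depends on each volunteer's cooperation. No screen, separate preparation area or masked syringe is described, and asking volunteers to look away during preparation implies that it takes place where they could see it.

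For reactogenicity the volunteer is the main observer. Keeping the vaccinator out of all other roles protects staff assessments but does nothing for diary scores. Someone who knows whether the adjuvanted or the plain product was given may report pain, fatigue or use of analgesics differently, and no later analysis can separate that from a real difference in tolerability. Section 9.2.7 also sends interim reactogenicity results to the Department of Health to inform vaccination strategy, so a distorted comparison could be used early.

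**Working it through.** The protocol states no figure for this point, so there is none to reproduce. The check has three steps.

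**1. Requirement against measure.** Sections 7.4 A and B require that the syringe and the vaccine's appearance go unseen. The measure in both is an instruction to the volunteer. There are two moments of exposure, drawing up and injecting. Preparing the dose elsewhere removes the first only; the filled syringe is still visible at injection unless its barrel is covered.

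**2. What can be seen, and which diary it can affect.**

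- Doses given: 360 subjects × 2 = 720, of which 180 × 2 = 360 are GSK.
- Mixings needed: 360 / 10 = 36 if every vial is fully used, and more if part-vials are discarded. Mixing is therefore only an occasional cue. The cues tied to each dose are colour and the needle change.
- The first diary is handed in at the Day 7 visit and the second dose is given on Day 21 (Section 8.1). A glance on Day 0 can affect both diaries; a glance on Day 21 can affect only the second.

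**3. How large the bias could be.** All inputs here except n are assumptions. Let the true reaction rate p be the same for both vaccines, with n = 180 per vaccine. A fraction f of one arm is unblinded and over-reports by b.

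- Spurious shift: s = f × b.
- Chance that a two-sided 5% test is significant in that direction: Φ[(s − 1.96·SE0)/SE1], where SE0 = √[2p̄(1 − p̄)/n], p̄ = p + s/2, and SE1 = √{[p(1 − p) + (p + s)(1 − p − s)]/n}. With no bias this is 2.5%.

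Worked case: p = 0.30, f = 0.25, b = 0.20. Then s = 0.05, SE0 = √(2 × 0.325 × 0.675/180) = 0.0494 and SE1 = √[(0.2100 + 0.2275)/180] = 0.0493. The argument is (0.05 − 0.0968)/0.0493 = −0.95, which gives about 17%.

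| f | b | shift s | chance of significance, p = 0.30 | p = 0.50 |
|---|---|---|---|---|
| 10% | 10 points | 1 point | 4.0% | 3.8% |
| 25% | 20 points | 5 points | 17.1% | 15.6% |
| 50% | 30 points | 15 points | 83.9% | 82.4% |

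The effect runs from negligible to decisive depending on f and b. The protocol gives neither and describes no check on whether volunteers stayed blind.

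**The case against.** The strongest reply is that this is not an error. The protocol names the hazard and sets the required outcome, and how a site achieves it could be left to local instructions. Nothing in Section 7.4 forbids preparing the dose elsewhere. That is fair as far as it goes, and preparation in the volunteer's view is implied rather than stated. But the protocol does specify a method, and a more reliable one is available at almost no cost.

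Two further limits stand in full. First, the primary endpoint is laboratory serology, which a volunteer's knowledge is unlikely to move, and part of the reactogenicity data is measured in millimetres or by thermometer. Second, under scenario B everyone enrolled first receives the vaccine that arrived first. Volunteers, especially site staff, may infer it from the date whatever is done about sight. Section 9.2.5.3 already accepts that comparisons under sequential allocation are non-randomised.

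Several stronger readings are tempting but unsupported:

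- A reader might infer that a single glance at either vaccination spoils every diary score. A glance on Day 21 cannot reach a diary returned at Day 7.
- A reader might count 720 preparations that each reveal the vaccine through mixing. One mixing serves 10 doses, and half the doses need none.
- A reader might infer from "We will approach staff in frontline areas" that most volunteers are health-care staff. Section 6.7.1 gives no share and also allows recruitment through GPs and advertising, and 120 of the 360 are aged 65 or over.
- A reader might attach a definite size, for example 10–20% unblinded with 20-point shifts in opposite directions, giving 0.10–0.20 × 40 = 4–8 points. The inputs are not in the protocol, and the opposite directions double the result by construction.

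**Conclusion.** The point holds as a weakness in the chosen blinding method. In both scenarios the only visual safeguard for the volunteer is an instruction to look away, although the protocol treats concealment of the dose as essential and the products look different. What is exposed is the between-vaccine comparison of self-scored reactions, a secondary objective, for the dose that was seen and any later dose.

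The size of the bias cannot be derived from the protocol. The 1- to 15-point range rests on assumed unblinding fractions, reporting shifts and baseline rates, and on bias in one arm only. It shows that the bias could be trivial or could dominate the comparison, not how large it will be. The documents do not support extending the concern to the serology primary endpoint, nor the view that better masking would make scenario B fully blind.

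**What to change.** Amend Sections 7.4 A and B so that:

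1. the existing un-blinded vaccinator mixes, inspects and draws up each dose out of sight of volunteers and blinded staff, behind a screen or in another room;
2. after inspection, the vaccinator covers the syringe barrel with an opaque sleeve or label before approaching the volunteer;
3. the instruction to look away stays as a secondary measure;
4. Section 7.4 B states that these steps close only the visual route, because allocation may still be inferred from the date of vaccination.

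Asking volunteers after each dose which vaccine they think they received would be a useful optional addition, so that the success of blinding can be reported.

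The cost is a screen, opaque tape and about a minute per dose. No extra staff are needed, and sample size, schedule and analysis are unchanged.
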